8.4 Accrual Goal and Accrual Period

To help safeguard 10 enrolling sites per intervention group (as originally proposed), we have invited more than 20 MU NCORPs/NCORPs to participate in this study (as listed on the cover page of the protocol). To further help accrual, we lowered the age limit to 15 years in Addendum 9 (effective from February 6, 2019). Besides the original participating MU NCORPs/NCORPs, interested pediatric MU NCORPs/NCORPs are allowed to participate in the EROS trial as well.

To have adequate power to detect the difference from 50% to 80% in the primary endpoint, the accrual goal of this study was re-calculated to ensure 149 patients in the intervention arm, assuming 16 sites enrolling patients for this trial (8 to the non-intervention group (Arm A) and the other 8 to the intervention group (Arm B)). Patients from each site will be enrolled into one of the four strata depending on the patient's pregnancy status, sexual activity status, and/or her birth intention. Given some sites accrue much faster than the others, a NCORP accrual cap of 45 patients was implemented per Addendum 8.

As of January 4, 2021, 268 patients from 9 Arm A sites and 138 patients from 8 Arm B sites have had been enrolled to this trial. As this is a comparative study, the trial will continue accrual for both arms until Arm B meets its accrual goal of 149 patients which is projected to take another 5 months. Taking into account the site accrual up to January 4, 2021 and the accrual rate in the past three months (i.e., the last three months of 2020, with the top three accrual sites met the accrual cap of 45 patients and closed accrual to Arm A), the final accrual of this study, thus, is expected to be 425 patients (276 from Arm A and 149 from Arm

Rev. Add11

Rev. Add8
Rev. Add9

B). The mean cluster size is projected to be 25 patients assuming 17 enrolling sites in total (~30 patients per cluster for Arm A and ~18 patients per cluster for Arm B). As suggested by Table 1, this study is equipped with more power if the cluster size is larger than the average of 18-19 patients per cluster and/or if the number of clusters per arm is greater than the stated 8 sites per arm in the sample size calculations. The additional patients and sites in Arm A imply the power of this study will be a little larger than stated (i.e., 85% power) to detect a change from 50% to 80% on the primary endpoint with the projected final accrual of 425 patients.

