8.6.4 Plan for Longitudinal Study of Sexuality

Measurement of PROMIS Sexual Function Survey Brief Profile v1.0 - Female will be used to evaluate the hypotheses that (1) cancer survivors' sexual function decreases during primary cancer treatment then increases after treatment completion and (2) cancer survivors have lower levels of satisfaction with their sex lives compared to the age-matched general population at baseline. All patients recruited for the EROS study will be included in this part of analysis. Data collected in PROMIS Sexual Function Survey Brief Profile v1.0 - Female in the EROS study will be summarized and plotted across time with respect to each of the subdomains (global satisfaction with sex life, interest in sexual activity, lubrication, vaginal discomfort, and orgasm). A linear mixed-effect model will be used to study changes in each of the subdomain scores of PROMIS Sexual Function Survey Brief Profile v1.0 - Female over time, with institution as the random effect (by stratum and across all patients if there is no difference between strata). For the secondary hypothesis, our comparative group is the

Rev. Add9

Rev. Add8

age-matched population of non-cancer females in the reproductive age range surveyed by the Duke Clinical Research Institute. The collaborator at Duke Clinical Research Institute will provide summary data on age-matched non-cancer patients. The PROMIS study uses a *T* score method with a mean of 50 and a standard deviation of 10. Results from the Sexual Function Survey in the EROS trial will be transformed into *T* scores as well then comparison between the groups will be performed using the two-sample *t* test.

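### The baseline comparison of T scores with the reference population ignores institution; if scores correlate within institution its standard error is too small, by an amount the documents do not fix

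*Combined protocol and SAP*

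**What the plan says.** Section 8.6.4 sets out two hypotheses for the sexual-function scores. The second is that "cancer survivors have lower levels of satisfaction with their sex lives compared to the age-matched general population at baseline". For this part, "All patients recruited for the EROS study will be included in this part of analysis". The comparison group is external: a collaborator "will provide summary data on age-matched non-cancer patients". Scores are put on the PROMIS metric, with "a mean of 50 and a standard deviation of 10", and then "comparison between the groups will be performed using the two-sample" t test. No cluster term is attached to that test, and no other section of the text reviewed adds one.

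In the same section, the model for change in the subdomain scores over time is fitted "with institution as the random effect". Section 8.6.1 uses GEE with the registering institution as the cluster for the primary endpoint. Section 8.3 builds within-cluster similarity into the sample size.

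Section 8.4 gives the sampling structure: "the final accrual of this study, thus, is expected to be 425 patients", and "The mean cluster size is projected to be 25 patients assuming 17 enrolling sites in total".

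**The concern.** An ordinary two-sample t test takes the standard error of the EROS mean as SD/√425. That is right only if two patients from the same institution are no more alike than two from different institutions. Baseline timing does not guarantee this, because similarity within sites need not come from the intervention. The protocol itself describes possible sources:

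- One designated research nurse or associate per institution runs the study and administers the questionnaires, unless the patient fills them in herself (Sections 5.4 to 5.6).
- Sites mix minority/underserved NCORPs, other NCORPs and interested pediatric programs (Sections 4.1 and 8.4).
- Any cancer type is eligible (Section 3.1.1), so case mix can differ by site.

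With positive correlation, the p-value is too small and any interval built from the same standard error is too narrow. The trial could then report lower satisfaction than the general population on weaker evidence than the stated test suggests. The external group arrives only as summary data, but that does not prevent a correction on the EROS side, where patient-level data with institution are available.

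**Working it through.** **Inputs from the documents**
- N = 425 recruited patients, 17 sites, mean cluster size m = 425/17 = 25 (Section 8.4).
- Cluster-size CV = 0.78 as of January 2021 (Section 8.3). The ratio is printed upside down there: 406/17 = 23.9 is the mean, so CV = 18.6/23.9 = 0.78. I assume that it holds at final accrual.
- SD = 10 on the T scale (Section 8.6.4). I use it for both groups; it cancels from the ratios below.

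**Assumptions, because the documents are silent**
- ICC of baseline scores: 0 to 0.05.
- Reference sample size: 100, 425, 1,000 or very large.
- Significance level: 5% two-sided. Section 8.6.4 states none; the 0.10 in Section 8.3 belongs to the primary endpoint.

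**Step 1. Check the design-effect formula against the plan's own power.** Section 8.3 states 85% power for 50% versus 80% with 8 clusters per arm, m = 15, CV = 0.8, ICC = 0.10 and two-sided α = 0.10.
- DEFF = 1 + [(1 + CV²)m − 1] × ICC = 1 + (1.64 × 15 − 1) × 0.10 = 3.36.
- SE = √[(0.25 + 0.16) × 3.36/120] = 0.107, and 0.30/0.107 = 2.80.
- With 14 df this gives power of 0.842 (shifted central t) or 0.845 (non-central t), against the stated 0.85.

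Agreement is less close in some other rows of that table. For example, the formula gives 0.879 to 0.883 where the plan prints 0.90 for m = 27. Step 4 therefore checks the result by simulation.

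**Step 2. Apply the same correction to the EROS mean.**
- DEFF = 1 + (1.6084 × 25 − 1) × ICC = 1 + 39.2 × ICC.
- Plain SE = 10 × √(1/425 + 1/n_ref).
- Clustered SE = 10 × √(DEFF/425 + 1/n_ref).
- r = clustered SE / plain SE.
- True error rate ≈ 2 × [1 − Φ(1.96/r)].

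Example with ICC 0.02 and n_ref = 1,000: DEFF = 1.78; plain SE = 0.579; clustered SE = 0.721; r = 1.25; error rate = 11.5%.

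**Step 3. Results** (each cell: SE ratio, true error rate of a nominal 5% test)

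| ICC | DEFF | Effective n | n_ref 100 | n_ref 425 | n_ref 1,000 | Very large n_ref |
|---|---|---|---|---|---|---|
| 0 | 1.00 | 425 | 1.00, 5.0% | 1.00, 5.0% | 1.00, 5.0% | 1.00, 5.0% |
| 0.005 | 1.20 | 355 | 1.02, 5.4% | 1.05, 6.1% | 1.07, 6.6% | 1.09, 7.3% |
| 0.01 | 1.39 | 305 | 1.04, 5.9% | 1.09, 7.3% | 1.13, 8.3% | 1.18, 9.7% |
| 0.02 | 1.78 | 238 | 1.07, 6.8% | 1.18, 9.7% | 1.25, 11.5% | 1.34, 14.2% |
| 0.05 | 2.96 | 144 | 1.17, 9.4% | 1.41, 16.4% | 1.54, 20.4% | 1.72, 25.5% |

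**Step 4. Simulation.** The plain t test was run 4,000 times per setting, with 17 unequal clusters (CV near 0.78) and 1,000 reference women. It rejected a true null in 4.8% of runs at ICC 0, 8.9% at ICC 0.01 and 19.9% at ICC 0.05. These agree with the table.

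**The case against.** The strongest reply is that nothing in the documents shows a material ICC for this outcome at this time. The only ICC given, 0.10, is for the primary endpoint, which concerns the adoption of appropriate management. The outcome here is a patient-reported score taken before chemotherapy, radiation or endocrine therapy. At an ICC of 0.001 the design effect is 1 + 39.2 × 0.001 = 1.04, and the test is practically at its nominal level. This stands. A reader might carry 0.10 across and conclude that the standard error is about doubled; the documents do not support that transfer.

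A reader might also take the institution random effect as an admission that baseline scores are clustered. It is not that. It sits in a model of change over time, in a trial that assigns the intervention by institution, so it would be needed even if the baseline ICC were zero. It shows that the plan has a suitable tool for these scores and does not use it in this test.

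A third reply is that the practical effect is small. With 1,000 reference women, the 95% half-width goes from 1.96 × 0.579 = 1.13 T points to 1.28, 1.41 or 1.75 at ICC 0.01, 0.02 or 0.05. In that scenario, an observed difference above about 1.8 points (0.18 SD) is declared either way. This also stands: only small differences would change verdict.

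None of these replies supplies a reason to assume independence. They limit the size of the problem, not its direction.

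**Conclusion.** The point holds in conditional form. The test named in Section 8.6.4 has no allowance for institution, and if the baseline ICC is above zero its standard error is too small. For an assumed ICC of 0.01 to 0.05 and a nominal 5% level, the error rate ranges from about 6% (ICC 0.01, 100 reference women) to about 25% (ICC 0.05, very large reference sample). The high end needs both the larger ICC and a reference sample so large that its own variance is negligible.

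Two stronger readings should be avoided. The first is that the test is known to be badly anti-conservative: with an ICC near zero it is close to nominal, and with a small reference sample the inflation is modest. The second is that the trial's main result is affected. This is the secondary hypothesis of an observational quality-of-life objective. The primary comparison already uses GEE clustered on institution, and the sample size does not rest on this test.

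One limit: Section 8.1 refers to an Addendum II for endpoint details, which is not part of the text reviewed. If it already specifies a cluster adjustment for this comparison, the point falls away.

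**What to change.** Replace the plain t test in Section 8.6.4 with two steps:

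1. Estimate the EROS baseline mean T score and its standard error with institution as a random effect, or as a simple mean with a cluster-robust standard error and a small-sample correction (about 17 − 1 = 16 df). Name one of these in advance, because the two weight large and small sites differently.
2. Compare that mean with the supplied reference mean and its standard error by a Welch-type test.

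The same paragraph should state the significance level and sidedness. It should also ask the collaborator for the reference sample size and standard error along with the mean, and the observed ICC should be reported with the result.

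The cost is a sentence or two in the plan. No new data are needed from patients, and the random-effect approach is already used in the section. The interval becomes somewhat wider. If the ICC proves to be near zero, little is lost beyond the smaller degrees of freedom.

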8.7 Randomization Scheme

Rev. Add8

Institutions that are selected to participate will be randomly assigned (with a 1:1 allocation ratio) to either the non-intervention arm or the intervention arm.

8.8 Monitoring Plan

Rev. Add8

Study Progress and Safety Reports are prepared twice yearly for all ECOG-ACRIN studies. Reports of these analyses are sent to the ECOG-ACRIN Principal Investigator or Senior Investigator at the participating institutions. The ECOG-ACRIN Data Safety Monitoring Committee (DSMC) will semi-annually review this randomized trial as well.

Rev. 11/16

An interim analysis plan is proposed to monitor study progress instead of early stopping for efficacy or futility.

The survey compliance rates (considering both Medical Record Abstraction Form and Patient Interview Form are completed), considering both baseline/3 months and baseline/6 months will be reported separately in each of the interim analysis, starting after every 100 patients enrolled on this study and synchronizing with the DSMC meeting. The proportion of patients who adopts appropriate reproductive health management within 3 months from baseline visit (the primary endpoint, across all evaluable patients) will also be reported in the interim analysis, together with the 90% confidence interval. All these results will be presented to the DSMC.

8.9 Race and Ethnicity

Rev. 11/16
Rev. 11/17

Rev. Add8

Patients in this study will be females only. The slow accrual in Arm B led to over-accrual in Arm A (n=268, as of January 4, 2021) with respect to the new accrual goal (n=149 per arm). Taking into account the site accrual up to January 4, 2021 and the accrual rate in the past three months (i.e., the last three months of 2020), the final accrual of this study is projected to be approximately 425 patients in total when Arm B meets its accrual goal. According to historic data for ECOG studies (E5103, PACT1, E4599, E4402, and E1A11), the anticipated accrual in subgroups defined by ethnicity and race is as follows:

Racial Categories	Not Hispanic/Latino		Hispanic/Latino		Total
	Female	Male	Female	Male	
American Indian/Alaska Native	2	0	0	0	2
Asian	14	0	0	0	14
Native Hawaiian or Other Pacific Islander	2	0	0	0	2
Black or African American	43	0	2	0	45
White	315	0	47	0	362
Total	376	0	49	0	425

The accrual targets in individual cells are not large enough for definitive comparisons to be made within these subgroups. Therefore, overall accrual to the study will not be extended to meet individual subgroup targets.

8.10 Handling Missing Data

The primary analysis will treat missing data as missing at random then analyze cases with complete data. The method of multiple imputation will be used to handle missing data if more than 20% of the cases have missing data in the variables of interest. If so, sensitivity analysis will be performed to compare results from the complete case analysis and imputation analysis. In case of discrepancies, possible explanations will be discussed. For longitudinal data, given the expected high level of missingness in these data, data will be analyzed according to the methods described in Schluchter and in Schluchter, Greene, and Beck^{28,29}. These methods take into account the possibility of informative missingness by jointly modeling the longitudinal response and the time to dropout.

9. Correlative Studies

NOTE: Effective March 10, 2021 the endocrine marker sub-study is closed to further accrual. This sub study has met its targeted accrual goal.

Serum specimens should continue to be collected from previously enrolled patients that have consented to provide serum specimens at the time points outlined below.

Do not submit serum specimens from patients registered to E1Q11 after March 10, 2021.

NOTE: THIS SECTION APPLIES TO BOTH STUDY ARMS.

Rev. 5/17

NOTE: ECOG-ACRIN requires that all biological samples submitted be entered and tracked via the online ECOG-ACRIN Sample Tracking System. An STS shipping manifest form must be generated and shipped with the sample submissions. See Section [9.4](#).

NOTE: An informed consent must be signed prior to the submission of any samples for laboratory studies. Samples for the optional laboratory studies should be submitted only from patients who have given written consent for the use of their samples for these purposes.

9.1 Study-Specific Account Set Up for Quest Diagnostics

The following steps should be completed prior to consenting or registering patients to the study, as account creation and initial supply delivery takes about two (2) weeks.

- Institutions must complete and submit the Quest Diagnostics Sub-Account Information Sheet ([Appendix III](#)) to create their study-specific account number.
- E-mail the completed form to [contact] or Fax to [contact].
- Quest will provide each institution with a study-specific account name and number and ship an initial allocation of supplies (collection tubes, specimen labels, specimen transport bags, serum transport vials/caps, pre-printed custom requisitions forms) using the contact information listed on Account Set Up Information section of the Sub-Account Information Sheet ([Appendix III](#)). The study-specific account number will be included on a laminated form with the initial supplies shipment.
- Upon receipt of the study-specific account number, institutions should contact Quest at [contact] to obtain courier and pick-up details for their institution. Institutions will be given a specific cut-off time for calling in to receive same day pick-up and to determine if Saturday service is available (if needed). The courier service will provide dry ice. If your institution is not eligible for Quest courier pick-up Quest will provide supplies for shipping via FedEx.
- To order additional supplies contact Quest Diagnostics at [contact] or e-mail [contact]. Supplies will be shipped via ground delivery to arrive within three to five working days.

Rev. 5/17

9.2 Sample Submission Schedule

Blood samples are being collected for the correlative studies outlined in Section [1.7](#) and analyzed by Quest Diagnostics.

NOTE: Results of these laboratory tests will not be returned to the institutions or reported to the patient.

NOTE: Blood samples should be collected as outlined in the table and sections below.

Rev Add 11

Biological Materials	Day of Registration [prior to treatment] ¹	Within One Week Prior to Start of Each Chemotherapy Regimen or Every Four Weeks during RT ¹	At the end of 3, 6, 12, 24 Months from Baseline Visit

From Patients Who Answer "Yes" to "I agree to participate in the laboratory research studies that are being done as part of this clinical trial."³
			
Serum (one 7.5mL red top tube) ²	X	X	X
Serum, SST (one 7.5mL red/black top) ²	X	X	X

1. For patients undergoing chemotherapy, blood samples will also be collected in conjunction with chemotherapy within one (1) week prior to the start of each chemotherapy regimen. For patients undergoing radiation therapy (RT) alone, blood samples will be collected within one (1) week prior to the initiation of radiation therapy and every four (4) weeks until the end of radiation treatment.
2. When possible, blood draws will be timed with the collection of blood draws for routine clinical purposes thus minimizing participant burden.

Rev. 5/17

9.3 Sample Preparation Guidelines

If you have any questions concerning sample collection and shipment, please contact Quest Diagnostics National Clinical Call Center at [contact] or [contact] Monday-Friday 7AM-7PM CST, please have your national account number ready when calling.

Rev. 5/17

9.3.1 Red Top Tube Collection

1. Draw 7.5mL of blood into the Red Top tube.
2. Invert tube gently no more than eight (8) times to mix the blood with the clot activator.
3. Do not remove stopper at any time. Do not centrifuge immediately after drawing blood. Allow the blood to coagulate in an upright position at room temperature for at least 30 minutes, but no longer than one (1) hour before centrifugation.
4. Centrifuge tube for at least 15 minutes at speeds between 2200 and 2500rpm within one (1) hour of collection.
5. Separate serum from clot and dispense at least 1mL of serum into the plastic transport screw cap vial.

Rev. 5/17

6. Screw the cap to the vial securely and freeze at $\leq -20^{\circ}\text{C}$ immediately until pick-up.

9.3.2 SST Tube Collection

1. Draw 7.5mL of blood into the SST tube.
2. Invert tube gently no more than eight (8) times to mix the blood with the clot activator.
3. Do not remove stopper at any time. Do not centrifuge immediately after drawing blood. Allow the blood to coagulate in an upright position at room temperature for at least 30 minutes, but no longer than one (1) hour before centrifugation.
4. Centrifuge tube for at least 15 minutes at speeds between 2200 and 2500rpm within one (1) hour of collection.
5. Store at ambient temperature until pick-up.

Rev. 5/17

9.3.3 Labeling and Custom Test Requisition Form Completion

All specimens should be labeled at the time of collection with at least two patient identifiers.

Each tube must be clearly labeled in ball point pen to include:

- ECOG-ACRIN Five-Digit Patient Sequence Number (required, if not available at baseline visit Patient Initials must be used)
- Patient Gender

The tubes must also be labeled with the specimen labels from the test requisition forms. See packaging guidelines below.

Specimens must be accompanied by custom paper test requisition forms. Custom test requisition forms will be included with the supplies. Two pre-printed test requisition forms must be submitted with the blood samples (one for each tube type).

Complete the patient information section on the requisition and select the tests to be performed. Please be sure to keep a copy of each test requisition form within the patient's chart.

The tests to be ordered with corresponding codes are as follows:

Frozen Red Top Tube

- Anti-Mullerian Hormone AssessR [#37227]

Ambient SST Tube

- Thyroid Peroxidase Antibodies (TPO) [#5081]
- TSH [#899]
- FSH [#470]

The requisition should contain the following patient information:

- ECOG-ACRIN Five-Digit Sequence Number (enter under Patient ID#) (if not available at baseline visit Patient Initials must be used)
- Do NOT write in the patient's name
- Sex
- Name of Insured/Responsible Party (enter as ECOG-ACRIN)

- Name and Address of Physician Ordering the Test
- Tests Requested (see codes above)
- Date and Time of Specimen Collection
- Fasting or Non Fasting

Please do NOT fill out information related to results reporting, patient social security number and date of birth, patient phone number and street address.

9.3.4 Packaging Guidelines

1. Ensure that all specimen container caps and lids are properly tightened to prevent leakage.
2. Complete the test requisition forms, one for the frozen blood sample in the transport tube and one for the blood sample in the SST tube.
3. Collect the specimens and transfer to a proper transport container, if needed.
4. Double check the specimen container to ensure that the device is not beyond its stated expiration date.
5. Remove a self-stick label from the bottom of the pre-printed paper test requisition and securely affix this label to the specimen transport container. Fold the top copy (original) of the test requisition in half widthwise (top to bottom) with the bar code facing out. Retain the second copy for your files.
6. The specimen transport bag has two pouches. Place the specimen containers in the front pocket. Insert the test requisition into the rear pocket with the bar code visible in the bottom corner of the bag.
7. Frozen specimens should be transported in plastic screw--cap containers only. Frozen specimens must be placed in a separate specimen bag along with a separate test requisition.
8. Remove the protective strip and seal the specimen bag. The protective strip must not obstruct the bar code. This will protect the test requisition from leakage and help ensure that the patient information can be entered directly into the laboratory computer by scanning of the bar code.

Rev. 5/17

